8.4 Analysis Sets

Intention-to-Treat Analysis Set (Full Analysis Set)

The Intention-to-Treat (ITT) Analysis Set will include all subjects randomly allocated to a treatment, based on the intention to treat “as randomized” principle (i.e., the planned treatment regimen rather than the actual treatment given in case of any difference).

Modified Intention-to-Treat Analysis Set

The Modified ITT (mITT) Analysis Set will include all subjects from the ITT Analysis Set who have a baseline and at least one post-treatment MRI assessment available.

Per-Protocol Analysis Set

The Per-Protocol (PP) Analysis Set will include all subjects from the mITT Analysis Set who have been treated according to the clinical trial protocol and fulfill the following criteria:

- Compliance with all entry criteria
- Absence of major clinical trial protocol violations with respect to factors likely to affect the efficacy of treatment, where the nature of such clinical trial protocol violations will be defined before breaking the blind
- Adequate compliance with trial medication (this will be defined in the SAP)

Safety Analysis Set

The Safety Analysis Set will include all subjects who receive at least one dose of trial treatment. Subjects will be analyzed according to the actual treatment they receive.

Pharmacokinetic Analysis Set

The PK Analysis Set will include all subjects from the Safety Analysis Set with at least one available serum or synovial fluid measurement.

Subgroup Analyses

Subgroup analyses (especially for the analysis of the primary endpoint) will be considered for categories including Kellgren-Lawrence grade (Grade 2, Grade 3), sex (Male, Female), age (< 65 years old, \geq 65 years old), body mass index (BMI; < 30 kg/m², \geq 30 kg/m²), and country.

8.5 Description of Statistical Analyses

8.5.1 General Considerations

An outline of the analysis currently planned is presented in the following sections. The full documentation will be provided in the Statistical Analysis Plan (SAP), which will be finalized before database lock and unblinding.

It is planned to perform the statistical analysis in two steps. Approximately three months after the last subject's last visit of the DBPC treatment phase, the database will be locked, the treatment code will be unblinded, complete analyses will be performed, and a detailed Clinical Trial Report will be written based on the data collected up to the end of the DBPC treatment phase. Long-term follow-up data will be analyzed and reported separately from the DBPC treatment phase results. MRI readers, Investigators, and subjects will remain blinded during the extended follow-up phase.

Summary Statistics

The summary statistics presented for quantitative variables will be the number of observations (n), the number of missing values (missing), mean, standard deviation (SD), median, first and third quartiles (Q1, Q3), and minimum (min) and maximum (max) values.

The summary statistics presented for categorical data will be the number of observations (n), the number of missing values (missing), and the count and percentage of subjects in each category.

Adjustment for Multiplicity

The main objective of this Phase II trial is to select a dose regimen for further development in Phase III; therefore, no adjustment for multiplicity will be made. Caution should be used in interpreting significant p-values ($p < 0.05$). Interpretation of the results will involve global consideration of all efficacy results obtained in combination with an appropriate judgment of clinical significance.

Missing Data

As a general rule, all data collected and available will be used in the analysis. No imputation of missing data will be applied independently of the statistical method used to analyze the data.

Handling of missing data from questionnaires will depend on whether only single items are missing or a complete questionnaire is missing. If only single items are missing, the rules defined by the authors of the questionnaires (if any) will be followed. If a complete questionnaire is missing, different methods of imputation will be used and results will be compared in a sensitivity analysis.

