5.1 Overall Trial Design and Plan

This is a multicenter, randomized, double-blind, placebo-controlled, parallel-group Phase II trial of sprifermin administered i.a. in subjects with primary OA of the knee and Kellgren-Lawrence grade 2 or 3.

The trial will randomize approximately 545 subjects (109 per treatment group); sample size calculations are described in Section 8.1.

The trial consists of a screening period lasting up to 42 days, a 2-year (104-week) double-blind placebo-controlled (DBPC) treatment phase, which will start at randomization (Week 0/Visit 2), and a 3-year extended follow-up phase (see [Figure 1](#) and [Figure 2](#)).

Figure 1 Trial Schema: Screening and DBPC Treatment Phases

Abbreviations: W: Week; MRI: magnetic resonance imaging; WOMAC: Western Ontario and McMaster Universities Osteoarthritis Index; PGA: Patient's Global Assessment; KOOS QOL: Knee Injury and Osteoarthritis Outcome Score quality of life subscale; KOOS Symptom Index: Knee Injury and Osteoarthritis Outcome Score symptom index subscale; PGIC: Patient's Global Impression of Change; NRS pain score: numerical rating scale pain score; MOS SF-36: Medical Outcomes Study Short Form-36 General Health Survey; ICOAP: Measure of Intermittent and Constant Osteoarthritis Pain.

[figure not shown]
Each treatment cycle consists of one i.a. injection per week for 3 consecutive weeks.

DBPC treatment phase visits will occur at Weeks 0 (randomization and first IMP injection), 1, 2, 3, 12, 26, 27, 28, 29, 38, 52, 53, 54, 55, 64, 78, 79, 80, 81, 90, and 104.

Pain medications must be withheld for at least 5 half-lives before a visit involving completion of the WOMAC.

Adverse events, concomitant medications, and concomitant procedures (including concomitant surgical procedures on the target knee) will be monitored throughout the trial. Time points for safety, laboratory, PK, and biomarker assessments are shown in [Appendix E](#).

Figure 2 Trial Schema: Extended Follow-up Phase

- ▲ MRI, X-ray, WOMAC, PGA, KOOS QOL, KOOS Symptom Index, PGIC, NRS pain score, pain in other joints, MOS SF-36, ICOAP, 20-meter walk test
 - △ WOMAC, PGA, KOOS QOL, KOOS Symptom Index, PGIC, NRS pain score, pain in other joints, MOS SF-36, ICOAP, 20-meter walk test.
- Safety will be assessed at all visits.

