5.2 Discussion of Trial Design

Overall Trial Design

The trial will consist of a screening period, a 2-year DBPC treatment phase, and a 3-year extended follow-up phase.

A screening period of up to 42 days is considered appropriate for assessment of subject eligibility. The screening period will include an assessment of pain levels at screening and baseline prior to randomization. The subject must have a pain score in the target knee of 4 to 9 in response to Question 1 of the WOMAC after a predefined washout period that will be equivalent to at least 5 half-lives of analgesic medication(s) to be eligible for the study (see Section 5.4).

The duration of the DBPC treatment phase of the trial will be set at 2 years in order to permit assessment of potential symptomatic and structural benefit. Results of the POC trial suggested that a period longer than 1 year would be necessary to observe treatment benefit on symptoms relative to placebo resulting from the demonstrated anabolic effect on structure.

The extended follow-up phase is intended to permit evaluation of the durability of the effects of sprifermin.

Sprifermin may be the first drug used in OA to have a disease-modifying action. In the absence of an active comparator, placebo will be used as a control.

A considerable placebo effect on symptoms in OA trials (with an effect size of 0.5 and a duration of 1 year) has been described in the literature (16), and was observed in the POC trial. In this trial, use of pain medication will be controlled to permit greater consistency of pain and function evaluations and eliminate the confounding effects of concomitant analgesia: subjects will need to refrain from taking analgesics, anti-inflammatory medications, or corticosteroids for ≥ 5 half-lives before a visit involving completion of the WOMAC. This requirement and the withdrawal of analgesic medication for 5 half-lives prior to pain assessments is a common practice in clinical trials in OA (17).

Subject Population

This trial will include symptomatic subjects who have sufficient residual cartilage to respond to sprifermin, and will include better control for external factors such as malalignment than the POC trial. The aim is to select a knee OA population where an improvement in structure may ultimately translate into improvements in symptoms and quality of life.

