6.5.3 Other Trial Considerations

Other Permitted Therapies

Patient education and physical or occupational therapy (e.g., assisting device for walking, diet for weight loss, muscle-strengthening exercises) are allowed.

Other Non-Permitted Therapies

Interventional or diagnostic arthroscopy affecting the target knee is not permitted.

Use of electrotherapy (e.g., transcutaneous electrical stimulation) or acupuncture for OA affecting the target knee is not permitted.

If any of these procedures are used during the trial, treatment with the IMP will be discontinued and the subject will be followed up as described in Section 7.1.5.

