The Intention-to-Treat (ITT) Analysis Set will include all randomized subjects and will be reported in any analysis "as randomized" i.e. only the planned treatment regimen is used. (i.e., the planned treatment regimen rather than the actual treatment given in case of any difference). This analysis set will be used for all non-MRI efficacy evaluations (symptoms and X-ray based endpoints).

Modified Intention-to-Treat Analysis Set

The Modified ITT (mITT) Analysis Set will include all subjects from the ITT Analysis Set who have a baseline (prior to first injection) and at least one post-treatment quantitative MRI assessment available in the DBPC part (up to and including day 819). This analysis set will be used for all MRI efficacy evaluations.

Per Protocol Analysis Set

The Per-Protocol (PP) Analysis Set will include all subjects from the mITT Analysis Set who have been treated according to the clinical trial protocol and fulfill the following criteria:

- Compliance with all entry criteria (fulfilling all inclusion criteria and no exclusion criteria)
- Absence of major clinical trial protocol deviations with respect to factors likely to affect the efficacy of treatment, such as non-missing and valid baseline and post-baseline measurement of the primary efficacy endpoint (quantitative MRI), where the nature of such deviations will be defined before or at the Blind Data Review Meeting (before breaking the blind) for the reporting of the treatment phase, in collaboration between the medical, clinical and statistical responsible person (see also Section 8).

Major protocol deviations affecting efficacy include: Prohibited medication/procedures during the treatment period and inadequate treatment compliance i.e. deviations from the planned amount of active dose and schedule of treatment (out of allowed window as specified in the "Analysis Sets" document). In order to be compliant the inter-cycle window should be within 140 to 196 days, and the intra-cycle window should be 5 days or above. Subjects who have (actual total dose)/(planned total dose)*100 within 75-100 % will be considered treatment compliant. If subject was randomized to placebo group but instead received at least one dose of sprifermin, then this subject will be classified as having major protocol deviation. A comprehensive list of all deviations and the process to identify each type of deviation are provided in the "Analysis Sets" document that will be finalized prior to Year-2 database lock.

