- 3. baseline mal-alignment in target knee (< -3 or > 3 or [-3,3] degrees)

Pain medications [classified for 3 timing groups defined in Section 14]:

- 1. Pain medications (Yes, No) any of 2, 3 or 4 defined below
- 2. Analgesics, Opiods in WHO ATC code group N02A (Yes, No)
- 3. Analgesics, Other analgesics and antipyretics in WHO ATC code group N02B (Yes, No)
- 4. Non-steroid anti-inflammatory and antirheumatic products in WHO ATC code group M01A (Yes, No)

Other subgroups:

Subgroups defined by SNPs and biochemical biomarkers cutoffs subgroups (see Section 16.4);

A listing of protocol-permitted concomitant pain medications and their respective washout times was provided in Appendix 19.2. Prior to unblinding this list may be updated.

Subgroups will be defined by individual listing prior to database lock and prior to breaking the blind for the reporting of the treatment phase.

11 General Specifications for Statistical Analyses

It is planned to perform the statistical analysis in two steps. Approximately one month after the last subject reaches day 819 of the 2-year DBPC treatment phase, the database will be partially locked, the treatment code will be un-blinded. Thereafter, complete analyses will be performed, and a detailed CTR will be written based on the data collected up to the end of the DBPC treatment phase (day 819). Long term follow-up data (from Year 2 to Year 5) will be integrated and analyzed with the DBPC treatment phase data but reported separately from the DBPC treatment phase results. Investigators, other site staff, study monitors, and subjects will remain blinded to study treatment during the extended follow-up phase as described in Section 8. X-ray and MRI readers will remain blinded to study treatment until completion of the extended follow-up phase results.

A list of endpoints according to treatment phase is provided in Appendix 19.1.

Summary Statistics

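### The WOMAC analysis states no strategy, and has no visit-level check, for scores taken inside the analgesic washout or after target-knee surgery or a prohibited injection

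*Protocol*

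**What the plan says.** **Washout.** Protocol 5.1: "Pain medications must be withheld for at least 5 half-lives before a visit involving completion of the WOMAC". Protocol 5.2 gives the reason: "use of pain medication will be controlled to permit greater consistency of pain and function evaluations and eliminate the confounding effects of concomitant analgesia". Under Protocol 6.5.1, paracetamol, NSAIDs and tramadol are otherwise permitted after randomization. Diaries collect pain-medication use (Protocol 7.1.1). SAP Section 10 adds: "A listing of protocol-permitted concomitant pain medications and their respective washout times was provided in Appendix 19.2".

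**Analysis.** Under the Missing Data heading, Protocol 8.5.1 and SAP Section 11 both say: "As a general rule, all data collected and available will be used in the analysis". SAP Section 10 assigns symptom endpoints to the ITT set, and SAP 16.2 fits the repeated-measures model to WOMAC change from baseline.

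**Prohibited treatments.** Intra-articular corticosteroid or hyaluronic acid (Protocol 6.5.2) and arthroscopy of the target knee (Protocol 6.5.3) lead to stopping study drug. SAP Section 10 counts as major deviations "Prohibited medication/procedures during the treatment period and inadequate treatment compliance", which exclude the subject from the Per-Protocol set. SAP 19.5.2 repeats the WOMAC total, pain and function outputs in that set.

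**Surgery and responders.** Protocol 8.5.4 promises a separate tabulation of target-knee surgery. SAP Section 14 provides only a listing of procedures, while SAP Appendix 19.1 marks them as descriptive. SAP 16.5 defines a WOMAC responder by a 10-point improvement at all timepoints including LOCF. In SAP Table 3, the second LOCF value takes the last measurement up to day 1849 (Month 60).

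**The concern.** The protocol wants WOMAC read free of analgesia, but the analysis cannot show whether it was. A score completed on an NSAID enters the model exactly like one completed off it. A score after knee replacement also stays in, since Protocol 5.5.1 does not list surgery among the reasons for mandatory withdrawal.

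Subjects in more pain are more likely to break the washout or to seek an injection or surgery. If that happens more often in one arm, that arm's scores improve because of treatments taken when the study drug helped less.

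The symptom result carries weight here. Protocol Section 3 says a positive trial should identify a regimen acting on both structure and symptoms. It also reports that in the proof-of-concept trial WOMAC improved most on placebo, a result needing further investigation. Differential analgesia is an obvious rival explanation for such a pattern, and the plan has no visit-level way to examine it. The same WOMAC scores also feed the structure-symptom correlations in SAP 16.5.

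**Working it through.** **1. What each existing safeguard covers**

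- *Per-Protocol set:* whole subjects are dropped for prohibited treatments in the treatment period. The visible text does not name a washout breach by a permitted analgesic, and arthroscopy is the only surgery that Protocol 6.5.3 prohibits by name. The set starts from subjects with MRI data, and the 20-meter walk is not among the listed repeats.
- *Stopping study drug:* under Protocol 7.1.5 the subject has the Week 104 assessments at once and then, if willing, Visits 23 to 28. Few later treatment-phase scores are therefore planned after an early event. An event after the last injection (Week 80) leaves Weeks 90 and 104 in place, and any event leaves years 3 to 5.
- *Pain-medication subgroups (SAP Section 10):* Yes/No by drug class and by broad timing group, descriptive, not tied to a WOMAC visit.
- *Corticosteroid rule (Protocol 6.5.2):* WOMAC is deferred by 5 half-lives after oral corticosteroids above 5 mg/day. I found no visit-level rule for any other drug.

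**2. The plan's own WOMAC power**

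Inputs from Protocol 8.1, Table 3: n = 76 per arm; SD 20 (total), 22 (pain), 21 (function). Two-sided 5% is assumed. Power = Φ(δ/SE − 1.96), with SE = SD × √(2/76). For the total score SE = 20 × 0.1622 = 3.24.

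- Total, 8/9/10 points: 69.4%, 79.2%, 86.9% (stated 69, 79, 87).
- Pain, 10/15 points: 80.0%, 98.8% (stated 80, 99).
- Function, 7/9/10 points: 53.8%, 75.2%, 83.5% (stated 53, 75, 83).

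The table reproduces within one percentage point. No stated figure is in question.

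**3. Possible shift (all rates and effects assumed)**

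Shift = difference between arms in the share affected × points gained per affected score.

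- Washout breach: (0.10 to 0.20) × (5 to 10) = 0.5 to 2.0 points.
- Target-knee replacement, years 3 to 5: (0.02 to 0.05) × (30 to 40) = 0.6 to 2.0 points.
- Equal shares and a constant gain: 0 points.
- Extreme corner: 0.20 × 30 = 6 points. Nothing in the documents supports inputs that large.

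**4. What that would do to WOMAC total at a true 10 points**

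- Shift 0.5: 9.5 points seen, power 83.4%.
- Shift 2.0: 8 points seen, power 69.4%.
- No true effect but a 2-point shift from any cause: two-sided rejection rate about 9.5% instead of 5%.

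**5. Responder tables**

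A subject with a replacement and a 30 to 40 point gain passes the 10-point rule. Coding that subject as a non-responder lowers the arm's rate by the share replaced. With a 2 to 5 percentage-point difference in replacement, the responder difference moves by the same 2 to 5 percentage points.

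**6. Cost of setting flagged scores to missing**

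If 10% to 20% of scores at a visit are flagged, n falls to 68.4 or 60.8 per arm. Power at 10 points on the total score falls from 86.9% to 83.2% or 78.7%. This is a single-visit approximation.

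**The case against.** A reader might infer that using all data is itself the error, so that WOMAC differences necessarily mix sprifermin with analgesia and surgery. The documents do not support that. The sentence is a missing-data rule, and analysing every observed score as randomized is a standard treatment-policy choice. A shift also needs unequal event rates, which the documents do not give. If the less effective arm has more events, the shift hides a true benefit rather than creating one.

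A reader might also infer that stopping study drug is the only consequence of a prohibited treatment. That is wrong too: Per-Protocol exclusion applies, with the main WOMAC outputs repeated. SAP 8.1 also lets a Blind Data Review Meeting exclude individual data before unblinding.

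Other points stand in part:

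- The deviation list in SAP Section 10 is not exhaustive. The full list is in a separate Analysis Sets document and may name washout breaches, although Per-Protocol exclusion would still act on subjects, not visits.
- The contents of Appendix 19.2 and the table shells are not in the available text.
- Concomitant pain medication is tabulated by arm (SAP 19.5.2), and the modelling in Protocol 8.5.5 may use it as a covariate. Neither links use to a WOMAC visit.
- Planned knee surgery within two years is an exclusion (Protocol 5.3.2), which limits early surgery but not later surgery.
- The 5-year efficacy evaluation is exploratory (SAP 8.2).
- Setting pain-driven breaches to missing at random is hard to defend as unbiased.

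The blinded review does not close the gap. SAP 8.1 gives it no criteria for these events and describes it only for the treatment phase. The code is broken at Year 2, so a rule for later scores made afterwards would be chosen with the arms known.

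**Conclusion.** The point holds in a limited form. The ITT WOMAC analysis can stay, but its strategy is undeclared. The visible plan cannot show how many scores were taken inside the washout or after target-knee surgery or a prohibited injection, or whether these differ by arm. The responder rule as written would credit a knee replacement as response.

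The size is not derivable from the documents. Under the assumed rates it is about 0.5 to 2 points on a 0-100 scale, against planned differences of 8 to 10 (total), 10 to 15 (pain) and 7 to 10 (function). It is zero if event rates and gains are equal between arms, and it would usually shrink a true benefit. By the same mechanism it could also mask a symptomatic disadvantage of the proof-of-concept kind. The primary MRI analysis is not at issue. This is a change that should be made because it is cheap and bears on what the trial can conclude about symptoms. It does not invalidate the planned analysis.

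**What to change.** Keep the ITT analysis as the main one and say in SAP 16.2 that it is a treatment-policy analysis of all observed scores. Then:

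1. Flag, at day level, each WOMAC visit with a listed analgesic inside its Appendix 19.2 washout time, and each score after target-knee surgery or a prohibited intra-articular injection. Tabulate the flags by arm and visit. For target-knee procedures, replace the listing in SAP Section 14 with a table by arm, as Protocol 8.5.4 promised.
2. Repeat the WOMAC and 20-meter walk models with flagged values set to missing, as a named sensitivity analysis. State that missing-at-random is doubtful when breaches are driven by pain.
3. In the WOMAC responder tables of SAP 16.5, count subjects after target-knee replacement as non-responders. Do not carry post-replacement scores into LOCF or present them as improvement in the 5-year summaries. Settle this before the Year-2 unblinding.

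The cost is SAP text, derived flags, one extra table and one extra model run. Some visit values are lost in the sensitivity run. The flags will be approximate: Protocol 6.5.1 asks for dose, frequency and duration but does not mention the time of last intake, and SAP Appendix 19.3 expects incomplete dates.

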8.5.2 Analysis of Primary Endpoint

The primary endpoint is the change from baseline in cartilage thickness in the total femorotibial joint as evaluated by MRI at 2 years.

The cartilage thickness in the total femorotibial joint as evaluated by MRI will be tabulated per time point (visit) and treatment group, along with the absolute change from baseline and the percent change from baseline.

The treatment effect on the primary endpoint will be assessed through dose-ranging using a repeated measurement analysis of variance (ANOVA, using PROC MIXED in SAS) on absolute change from baseline, including the baseline value, the treatment group, the time, and the country as factors and including treatment by time as interaction.

The primary efficacy analysis will consist of testing the linear dose relationship and the overall treatment effect at 2 years. The significance level will be set at 5% two-sided for both tests.

For the linear dose relationship testing, the null and alternative hypotheses will be:

$$H_0: -2 \text{ Mean}_{(\text{Placebo})} - 1 \text{ Mean}_{(180 \text{ mcg})} + 0 \text{ Mean}_{(360 \text{ mcg})} + 1 \text{ Mean}_{(600 \text{ mcg})} + 2 \text{ Mean}_{(1200 \text{ mcg})} = 0$$

$$H_1: -2 \text{ Mean}_{(\text{Placebo})} - 1 \text{ Mean}_{(180 \text{ mcg})} + 0 \text{ Mean}_{(360 \text{ mcg})} + 1 \text{ Mean}_{(600 \text{ mcg})} + 2 \text{ Mean}_{(1200 \text{ mcg})} \neq 0$$

where the doses shown are the total doses of sprifermin to be administered over the DBPC treatment phase (see [Table 1](#)).

If the null hypothesis is rejected, the alternative hypothesis will be accepted and it will be concluded that there is a dose relationship versus placebo over time.

For the overall treatment effect testing, the null and alternative hypotheses will be:

$$H_0: \text{Mean}_{(\text{Placebo})} = \text{Mean}_{(180 \text{ mcg})} = \text{Mean}_{(360 \text{ mcg})} = \text{Mean}_{(600 \text{ mcg})} = \text{Mean}_{(1200 \text{ mcg})}$$

$$H_1: \text{Mean}(i) \neq \text{Mean}(j) \text{ for some } i \neq j \text{ and } i, j = \text{Placebo or } 180 \text{ mcg or } 360 \text{ mcg or } 600 \text{ mcg or } 1200 \text{ mcg.}$$

where the doses shown are the total doses of sprifermin to be administered over the DBPC treatment phase (see [Table 1](#)).

If the null hypothesis is rejected, the alternative hypothesis will be accepted and it will be concluded that there is at least one group that differs from the other groups.

Pairwise comparisons (sprifermin versus placebo, and between sprifermin dose and regimen groups) will be performed within the context of this modeling framework. For each pairwise comparison, the difference between treatments and the corresponding 95% confidence interval (CI) and p-value will be presented.

The primary efficacy analysis will be performed on the mITT Analysis Set.

In order to assess the robustness of the primary results, sensitivity analyses will be performed with modification of subject population (PP Analysis Set), statistical methods (influence of the distribution, influence of the time effect, and so on), and influence of covariates.

